4.1 Rationale for study design

This is a single-arm, non-randomized, open-label phase IV clinical trial aimed to identify innovative early imaging parameters that could predict the long-term clinical response to

brolucizumab, in terms of fluid resolution, in patients affected by wAMD with the purpose to evaluate their potential in supporting the treatment regimen choice (q12w or q8w) after the loading phase.

The safety and efficacy of brolucizumab has been recently demonstrated in two randomized, multicenter, double-masked, active controlled Phase III studies in wAMD patients (RTH258-C001 [HAWK] and RTH258-C002 [HARRIER]) up to 96 weeks, as described in [Section 1.1](#). In these studies, anatomical changes were evaluated using SD-OCT, which relies on indirect parameters for the diagnosis and monitoring of active CNV.

Concurrently, research has led to a substantial development and/or improvement of cutting-edge imaging techniques in order to ensure the proper management of macular pathologies. The use of diagnostic imaging in the context of wAMD has allowed to define pathology indicators which can be evaluated in a more objective and reproducible manner, compared with visual acuity (VA).

In particular, OCTA has been widely introduced in ophthalmology clinical practice. OCTA is a diagnostic tool that allows the retinal and choroid vessels to be viewed dynamically. In OCTA, the contrast medium is the blood itself within capillaries, thus preventing the use of contrast medium to be injected intravenously and the risk of side effects proper of classical FA. In addition, available OCTA software automatically analyze retinal layer scans at different depths, providing more detailed images compared with less recent imaging techniques.

Several independent studies have been instrumental to understand and acknowledge the clinical relevance of OCTA for the qualitative and quantitative assessment of CNV lesions as an additional tool to evaluate the response to treatment in wAMD patients. This also provides promising evidence to suggest OCTA as relevant in treatment regimen decision, which generally relies only on the presence or absence of fluid on OCT B-scans.

A detailed multimodal imaging will be performed in this study to assess the predictive value of early anatomical parameters up to Week 16 for the long-term clinical response to brolucizumab in terms of fluid resolution and treatment regimen.

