8.3 Efficacy

The following assessments will be performed to assess the predictive value of early anatomical parameters measured by multimodal imaging at each visit from Baseline to Week 16 in q12w fluid-free participants (i.e. participants without IRF and SRF at Week 48 who have maintained a stable q12w treatment regimen up to Week 48 after the loading phase), as well as to evaluate the effect of brolucizumab on visual function, retinal structure, vascular leakage, quality of life and anxiety and depressive status:

- CNV lesion type assessed by FA, CFP and ICGA at Screening and SD-OCT at Baseline
- OCTA parameters, of which the main quantitative parameters are CNV flow size and vessel density and the main qualitative ones are branching vessels, peripheral anastomotic arcades, vascular loops and dark halo (from Baseline to Week 48)
- SD-OCT parameters, of which the main quantitative parameters are CRT and PED volume, and the main qualitative ones are IRF, SRF, sub-RPE fluid, status of the ELM, SHRM and outer retinal tubulation (from Baseline to Week 48)
- FA and ICGA (at Screening and Week 48)
- 3-field CFP (from Baseline to Week 48)
- BCVA with ETDRS-like charts at 4 meters (from Baseline to Week 48)
- EQ-5D-5L questionnaire (at Baseline and Week 48)
- HADS questionnaire (at Baseline and Week 48)

All efficacy assessments should be performed prior to any administration of study treatment.

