2. STUDY OBJECTIVES AND ENDPOINTS

| OBJECTIVES | VARIABLES | ENDPOINTS |
|--|---|---|
| 
Primary objective(s):
 
The primary objective is to assess the predictive value of early anatomical parameters measured by multimodal imaging from Baseline to Week 16, in brolucizumab-treated participants with wAMD who present fluid resolution (i.e. absence of IRF and SRF) at Week 48 and have maintained the q12w treatment regimen up to Week 48 after the loading phase, defined also as fluid-free response (q12w fluid-free participants), compared with participants under a more frequent regimen and/or not fluid-free at Week 48.
 | 
To define the outcome of interest:
 
 • Intraretinal fluid (IRF) based on SD-OCT at Week 48 • Subretinal fluid (SRF) based on SD-OCT at Week 48 • Regimen assigned and followed during the study 
The following variable will be considered as predictive factors:
 
 1. Basal CNV lesion type (i.e., Type of predominant CNV lesion) 2. SD-OCT Parameters at each visit from Baseline to Week 16: 
 • Sub-retinal pigment epithelium (sub-RPE) fluid • Subretinal Hyperreflective Material (SHRM) • Outer Retinal Tubulation (ORT) • ELM integrity loss in center 1 mm • Type of PED • Center Subfield Thickness (CST) | 
Primary endpoint(s):
 
Early predictive factors of fluid-free response, which is defined as the absence of IRF and SRF (assessed by SD-OCT) at Week 48 in patients with a stable q12w treatment regimen up to Week 48 after the loading phase.
 
The variables considered as potential predictive factors in the statistical model will be selected among the following qualitative and quantitative anatomical parameters:
 
 1. Basal CNV lesion type (i.e., Type of predominant CNV lesion), as assessed by SD-OCT at Baseline and FA, ICGA and CFP at Screening 2. Parameters assessed by SD-OCT at each visit from Baseline to Week 16, of which the main are presence/absence of sub-RPE fluid, subretinal hyperreflective material (SHRM), outer retinal tubulation, status of the External Limiting Membrane (ELM) and measurement of central retinal thickness (CRT) and type of PED |

| | |
|--|----------------------------------|
| | Statistical Analysis Plan |
| | Sponsor: Novartis |
| | Protocol: CRTH258AIT04 |

| OBJECTIVES | VARIABLES | ENDPOINTS |
|--|---|--|

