6.3. Efficacy Evaluation

6.3.1. Primary efficacy analysis

Definition of primary endpoint

The primary aim of the study is to assess which early anatomical parameters measured by multimodal imaging at each visit from Baseline to Week 16, predict in brolucizumab-treated participants with wAMD the q12w fluid-free response at Week 48.

The primary estimand of the study is to identify the q12w fluid-free predictive factors.

Patient will be classified as follows for the outcome of interest:

- **q12w fluid-free:** patients completing the treatment and the study maintaining a stable q12w regimen assigned at Week 16 up to Week 48 and without the presence of IRF and SRF at Week 48 according to SD-OCT grading.
- **not q12w fluid-free:**
 - patient who completes the treatment and the study with the presence of IRF or the presence of SRF at Week 48 according to SD-OCT grading;
 - patient who followed the q8w regimen of treatment at any time during the study (considering also who started with q12w regimen but then due to disease activity shifted to q8w regimen);
 - patient who discontinued treatment at any time after baseline since also the discontinuation from the treatment can be considered as intercurrent event and according to data handling rules should be considered as 'failure'.
 - patient who dropped out at any time after baseline since the discontinuation from the study is considered as intercurrent event and according to data handling rules should be considered as 'failure'.

The following qualitative and quantitative anatomical parameters measured by FA, ICGA, CFP and SD-OCT will be considered as potential predictive factors in the statistical model and, when measured at more than one timepoint, categories variables based on their changes between baseline and Week 16 will be created as described below:

| | |
|--|---|
| | Statistical Analysis Plan |
| | Sponsor: Novartis Protocol: CRTH258AIT04 |

| Variable | Timing of data collection | Source | Categories used in the model | Reference value for the model |
|----------------------------------|---|--|--|-------------------------------|
| Type of predominant CNV lesion | Screening | CRC grading based on SD-OCT, FA, ICGA and CFP at Screening | Type I, Type II, Type III, PCV, UNG/P or UNG/Q. Of note, Type I and PCV will be considered as unique category while UNG/P and UNG/Q will be considered as missing data. | Type I + PCV |

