NA=Not Applicable; CNV=Choroidal Neovascularization; UNG/P=Ungradable due to pathology; UNG/Q=Ungradable due to quality SHRM=Subretinal hyper reflective materia; ORT=Outer retinal tubulation; ELM=External Limiting Membrane; CST=Center Subfield Thickness; PED=Pigment Epithelial Detachment.

Of note, for each variable 'Missing' values can be present in case that images are collected but not graded by Central Reading Center (CRC) since they are collected by means of a not certificated instrument.

| | |
|--|----------------------------------|
| | Statistical Analysis Plan |
| | Sponsor: Novartis |
| | Protocol: CRTH258AIT04 |

Analysis methodology

Firstly, the proportion of patients with and without q12w fluid-free will be provided and then a descriptive summary table by q12w fluid-free and not q12w fluid-free will be provided for each variables described in table above.

A logistic models will be performed for each one of the variables listed above considering as outcome the patients' classification in q12w fluid-free and not q12w fluid-free.

Multivariable logistic model will be performed considering as outcome the patients' classification in q12w fluid-free and not q12w fluid-free and as covariates all the variables with $p<0.10$ in the previous analysis. Results of logistic models will be presented in terms of beta coefficient and standard error, Odds Ratio and relative 95% Confidence interval and p-value.

All these analyses will be performed on Safety population.

Data handling rules

In case of patients who dropped out at any time after baseline, the primary outcome cannot be evaluated since the patient status related to treatment regimen and presence of IRF o SRF at Week 48 are not observed. The dropped-out patients constitute intercurrent event and they will be considered a not q12w fluid-free at Week 48. Similarly, in case of patients who discontinued the treatment at any time after baseline, the primary outcome cannot be totally evaluated since the patient treatment regimen at q12w cannot be observed until Week 48. The patients who discontinued treatment constitute intercurrent event and they will be considered a not q12w fluid-free at Week 48.

Sensitivity of primary analysis

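### Early IRF and SRF are missing from the closed predictor list, so the planned analysis cannot show whether a selected marker predicts beyond early residual fluid

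*SAP*

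**What the plan says.** **Outcome.** SAP 6.3.1 classes a patient as q12w fluid-free if treatment and study are completed on a stable q12w regimen "without the presence of IRF and SRF at Week 48 according to SD-OCT grading". Failures include a "patient who followed the q8w regimen of treatment at any time during the study", as well as anyone who stops treatment or drops out.

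**Predictors.** The variables column of SAP section 2 opens with "The following variable will be considered as predictive factors" and names predominant CNV type, sub-RPE fluid, SHRM, outer retinal tubulation, ELM integrity loss, type of PED and CST. The table in SAP 6.3.1 has the same seven. IRF and SRF appear only as components of the outcome. The endpoint column, "Parameters assessed by SD-OCT at each visit from Baseline to Week 16, of which the main are presence/absence of sub-RPE fluid" and so on, is loosely worded, but the analysis text is not: "A logistic models will be performed for each one of the variables listed above". The multivariable model then takes as "covariates all the variables with $p<0.10$ in the previous analysis". The weighted sensitivity model reuses the covariates so selected.

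**Data available.** Protocol 8.3 says of the SD-OCT parameters that "the main qualitative ones are IRF, SRF, sub-RPE fluid, status of the ELM, SHRM and outer retinal tubulation". SAP 6.3.2.2 has the reading center grade IRF and SRF in the study eye at all visits except Screening. These gradings feed frequency tables, shift tables and McNemar tests (SAP 6.3.2.2) and sustained dryness (SAP 6.3.2.4). None of these relates early fluid to the primary outcome.

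**The concern.** Early IRF and SRF are the early values of the outcome's own fluid component. They may also act on its regimen component, because they are among the findings an Investigator may use to judge disease activity from Week 16. Protocol 4.1 describes the usual regimen decision as one "which generally relies only on the presence or absence of fluid on OCT B-scans", which makes early fluid the natural benchmark for any new marker. Protocol 1.1 adds that, in the pivotal trials, patients judged suitable for q12w in the first q12w interval had a greater than 80% probability of staying on it to Week 48. The planning assumption for all patients is 56%. That figure concerns disease activity rather than IRF and SRF alone, but it suggests that early status carries much of the information.

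The study's purpose is to find innovative parameters that could support the choice between q12w and q8w. A marker may reach significance because it tracks residual fluid or because it adds to it, and the planned models cannot separate the two. CST change and sub-RPE fluid are the obvious cases, since both can be expected to move with IRF and SRF.

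**Working it through.** **1. Is the gap filled elsewhere?**
- Univariable models: one per listed variable, so none for IRF or SRF.
- Multivariable model: only listed variables that pass the screen; no forced covariates.
- Weighted sensitivity model: same covariates.
- Week 16 regimen-choice model (SAP 6.3.2.5): its covariates are the categories of parameters the Investigator used, with IRF and SRF pooled under SD-OCT. It records that fluid was considered, not whether it was present.
- CST change: related to fluid, but not IRF/SRF status.

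No planned model contains early fluid.

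**2. How large could the proxy effect be?** The documents give no inputs, so these are assumed: residual fluid in 30%; response 20% with fluid and 65% without (0.30×0.20 + 0.70×0.65 = 51.5% overall, inside the plan's 46–56%); and a marker unrelated to response once fluid is known.

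Marker present in 70% of wet and 30% of dry eyes:
- Present: 0.30×0.70 = 0.21 wet and 0.70×0.30 = 0.21 dry. Response (0.21×0.20 + 0.21×0.65)/0.42 = 0.425; odds 0.739.
- Absent: 0.09 wet and 0.49 dry. Response (0.09×0.20 + 0.49×0.65)/0.58 = 0.580; odds 1.382.
- Odds ratio 0.739/1.382 = **0.54**; within each fluid stratum it is 1.

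Marker present in 85% and 15%:
- Present: 0.255 wet and 0.105 dry. Response 0.11925/0.36 = 0.331; odds 0.495.
- Absent: 0.045 wet and 0.595 dry. Response 0.39575/0.64 = 0.618; odds 1.620.
- Odds ratio 0.495/1.620 = **0.31**.

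**3. How often would such a marker be selected?** Simulated trials with N=122, 46% responders, fluid in 30% and 1,500 runs per scenario (all inputs assumed except N and the 46%). The fluid odds ratio is against response.

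| Fluid odds ratio | Marker in wet/dry eyes | Passes p<0.10 | p<0.05 unadjusted | p<0.05 with fluid in model |
|---|---|---|---|---|
| 1 | 70%/30% | 11% | 5% | 5% |
| 3 | 70%/30% | 26% | 16% | 5% |
| 6 | 70%/30% | 43% | 31% | 4% |
| 10 | 70%/30% | 56% | 43% | 5% |
| 3 | 50%/30% | 14% | 8% | 5% |
| 6 | 50%/30% | 18% | 11% | 5% |
| 10 | 50%/30% | 23% | 15% | 5% |

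The simulation has no other covariates. In the real multivariable model, CST change, if selected, could absorb part of the fluid signal. The univariable screen has no such protection.

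**4. Is there room for a fluid term?** The plan's limit of 12 covariates at N=263 reproduces with 10 outcomes of the rarer class per covariate: 0.44×263/10 = 11.6 at 56% responders and 0.46×263/10 = 12.1 at 46%. At N=122 the same rule gives 0.44×122/10 = 5.4 at 56%, 0.50×122/10 = 6.1 at 50% and 0.46×122/10 = 5.6 at 46%. The seven listed predictors need 2 (CNV type) + 5×3 (four-level variables) + 1 (CST) = 18 parameters if all were selected. One binary fluid term makes 19. IRF and SRF each in the SAP's four-level coding would make 24.

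**The case against.** The strongest reply is that the omission is deliberate. The primary predictor lists in both documents leave IRF and SRF out, while the secondary SD-OCT lists include them, and the stated objective is predictive value, not incremental value. For pure prediction an unadjusted odds ratio is not an error. This stands: the primary model is not wrong as a description of association, and the point concerns how its results may be read. It does not remove the need for the comparison, because a focus on innovative markers invites the question of what they add to standard information. Nor is the adjustment circular, since fluid up to Week 16 is not fluid at Week 48.

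Four stronger readings are tempting but unsupported:
- *The trial cannot answer the question.* The gradings are collected; only the planned models leave them out.
- *The SAP departs from the protocol.* The protocol's own predictor lists also omit IRF and SRF, and the list in Protocol 8.3 serves treatment-effect aims as well as prediction.
- *Adjustment would show value over what the physician sees.* Investigators do not see the reading center's results, their own imaging findings are not captured in the eCRF, and they may also use BCVA, CRT, sub-RPE fluid, hemorrhage, OCTA or CFP. Central IRF/SRF is a benchmark, not a record of the clinic decision.
- *Any marker found will be only a proxy.* Nothing in the documents shows this; it is a possibility that the plan cannot exclude.

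Cost is a fair objection too. The parameter budget is small, and SAP 1.1 reports many ungradable images, in SD-OCT and mainly in OCTA.

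**Conclusion.** The point holds as a limit on the planned analysis. Early IRF and SRF can enter none of the primary or sensitivity models, and no other analysis links them to the primary outcome. An odds ratio from these models may be reported as an association with q12w fluid-free response, but not as predictive value beyond early residual fluid.

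The size is unknown. The illustrative odds ratios of 0.54 and 0.31 for a marker with no effect of its own, and screen pass rates of 14% to 56% against 10–11% when fluid has no effect, rest on assumed fluid prevalence, response rates and marker–fluid links. If the link is weak, the distortion is small. The missing information is mainly fluid status at Weeks 4 to 16: IRF and/or SRF is required at Screening, so any-fluid status at Baseline should vary little. The addition is worthwhile and inexpensive, and the primary model need not change.

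**What to change.** Keep the primary model as written and pre-specify two additions:

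1. A univariable logistic model for early fluid, coded as any centrally graded IRF or SRF (yes/no).
2. One supportive model adding that single term to the final multivariable model. Report each predictor's odds ratio with and without it, fitted on the same patients.

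Score fluid at the last gradable SD-OCT up to Week 16, to match the other SD-OCT predictors; Week 16 imaging is taken before any injection at that visit. Repeat with Week 12 fluid as a check, because Week 16 findings may inform the regimen decision that is part of the outcome. Week 12 alone would leave fluid present at Week 16 unadjusted. Handle ungradable values as for the other SD-OCT predictors. State in the report that the benchmark is central grading, not the Investigator's reading.

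The cost is one parameter where the SAP's rule of thumb allows about 5 to 6 at N=122, leaving about 4 to 5 for the selected predictors, and possibly a few patients lost to ungradable images. Two four-level terms for IRF and SRF would not fit that budget. The model should therefore be labelled supportive.

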3. BACKGROUND AND RATIONALE

[figure not shown]
3.1. Overall Study Design and Plan Description

This is a one-year, open-label, single arm, multicenter, phase IV study that will be conducted at approximately 30 centers in Italy.

Patients with untreated active subfoveal Choroidal Neovascularization (CNV) secondary to wAMD who provide signed informed consent and meet all eligibility criteria will be included in the study. Approximately 300 patients are planned to be screened (12% screening failure rate expected) to enroll 263 evaluable participants. Enrolment was closed on October 2022, with 132 screened patients and 122 patients were enrolled. The duration of the study treatment for enrolled patient will be of maximum 48 weeks.

The study consists of a screening period of up to 2 weeks and of a treatment period with brolucizumab from Baseline (Day 1) up to Week 48 (refer to Figure 2.1-1).

Figure 2.1-1: Study design

* 44 or 48 weeks, depending on the treatment regimen implemented.

🕒 Disease activity assessment (DAA).

The first DAA is to be performed at Week 16, the others at each subsequent scheduled q12w/q8w treatment visit.

| | |
|--|----------------------------------|
| | Statistical Analysis Plan |
| | Sponsor: Novartis |
| | Protocol: CRTH258AIT04 |

3.2. Selection of Study Population

The study population includes male and female participants aged 50 years or older diagnosed with active subfoveal CNV secondary to wAMD in the study eye, not treated previously with any anti-VEGF drugs or investigational drugs (other than vitamin supplements) for this disease and able to comply with study procedures.

Since the focus of the study is on eyes, if both eyes are eligible as per the inclusion and exclusion criteria described in *Section 5.1 Inclusion Criteria* and *Section 5.2 Exclusion Criteria* of the study protocol only one eye should be treated during the study, the eye with the worse visual acuity (BCVA) at baseline will be selected as the study eye. If both eyes have the same BCVA, it is recommended to select the right eye as the study eye.

A complete list of all inclusion/exclusion criteria is provided in *Sections 5.1 Inclusion criteria* and *5.2 Exclusion criteria* of the study protocol respectively.

3.3. Treatment

3.3.1. Treatment Administered

The investigational drug is brolucizumab 6 mg in solution, administered by means of intravitreal (IVT) injection.

Brolucizumab will be provided in single use, sterile, pre-filled syringes. Each pre-filled syringe contains 19.8 mg brolucizumab in 0.165 ml solution. This provides a usable amount to deliver a single dose of 0.05 ml solution containing 6 mg of brolucizumab.

Since the volume contained in the pre-filled syringe (0.165 ml) is greater than the recommended dose (0.05 ml), a portion of the volume contained in the pre-filled syringe must be discarded prior to administration. To expel the air bubble along with excess medicinal product, the plunger should be slowly depressed until the edge below the dome of the rubber stopper is aligned with the 0.05 ml dose mark (equivalent to 50 μ l, i.e., 6 mg brolucizumab). Novartis will ensure sufficient supplies of brolucizumab for treatment use to allow for completion of the study.

[figure not shown]
No study treatment dose adjustment is permitted. Deviations to dose intervals during the initiation phase and/or dose adjustments during the whole study are not allowed. Interruption of study treatment is allowed if warranted by an adverse event.

As per Beovu® SmPC, the recommended dose of 6 mg brolucizumab (0.05 ml solution) is to be administered every 4 weeks (monthly) for the first 3 doses. Thereafter, the Investigator may individualize treatment intervals based on the disease activity in the study eye as assessed by visual acuity and/or anatomical parameters (BCVA and/or IRF,

| | |
|--|----------------------------------|
| | Statistical Analysis Plan |
| | Sponsor: Novartis |
| | Protocol: CRTH258AIT04 |

SRF, sub-RPE fluid, hemorrhage, CRT and/or OCTA parameters and/or 3-field CFP). A first disease activity assessment is to be performed at Week 16, as recommended in Beovu® SmPC. In participants without disease activity, treatment every 12 weeks (q12w) should be considered. In patients with DA, treatment every 8 weeks (q8w) should be considered. Disease activity will be first assessed at Week 16 and then at each subsequent scheduled q12w/q8w treatment visit. In participants on q12w regimen with disease activity at any of these visits, a q8w treatment regimen should be considered. In participants on q8w regimen without disease activity for two consecutive treatment visits in the opinion of the Investigator, the re-allocation to a q12w regimen should be considered. Figure 2.3.1-1 provides a graphical summary of the study drug administration during the study.

Figure 2.3.1-1: Treatment regimen

Regardless of treatment administration, Baseline, Week 4, Week 8, Week 12, Week 16 and Week 48 visits are mandatory for all participants. The timepoints of the other treatment visits will depend on the treatment regimen of each participant (q12w/q8w).

For all participants, the last potential study treatment will be at the Week 44 visit or at the Week 48 visit, according to the different treatment regimen implemented.

